Patients who receive the second administration of Bimatoprost SR at Week 16 and patients who never receive a second administration may, at the investigator's discretion, skip the visits at Months 13, 15 and 22 if the patient has received nonstudy IOP lowering medication in both eyes; has $\leq 25\%$ of each implant remaining in the eye; and in the investigator's clinical judgment, has no safety or other concern that would require the patient to attend these visits. Please note: as described in Section 4.5.2, each eye should be evaluated on an individual basis when determining the need for additional nonstudy IOP-lowering treatments; initiation of treatment in one eye should not automatically lead to initiation of treatment in the contralateral eye.

- Collection of adverse events
- Collection of concomitant medications and procedures
- Vital signs (at rest ≥ 5 minutes)
- Pregnancy test for females of childbearing potential (as defined in Section 4.5.3) (Month 24/Exit only)

The following procedures should be performed in both eyes (procedures in bold should be done in the order shown):

- **Pre-Hour 0 examinations** (may perform in any order before Hour 0 IOP):
 - Macroscopic conjunctival hyperemia assessment (The examination will also include [REDACTED]
[REDACTED]
[REDACTED] may be performed at interim visits for appearance of or increase/decrease in hyperemia.)
 - Best-corrected visual acuity
- **Intraocular pressure measurement at Hour 0**
- **Non-contact examinations:** The following may be performed in any order, at any time before gonioscopy (including prior to Hour 0 IOP):
 - Macroscopic iris color assessment (Week 52 and Months 18 and 24/Exit only)
 - Manifest refraction (Week 52 and Months 18 and 24/Exit only)

- Visual field (If dilation is required to perform this test, then the visual field test should be performed after the last IOP measurement of the day.) (Week 52 and Months 18 and 24/Exit only)
- Specular microscopy (Weeks 40 and 52 and Months 16, 20, and 24/Exit only)
- [REDACTED] (at Week 52 and Month 24/Exit at selected sites in both eyes of all consenting patients who underwent assessment at Screening; may be done at interim visits at the discretion of the investigator. Perform any contact assessments following IOP measurements.)
- Biomicroscopy (The examination will also include, [REDACTED]
[REDACTED]
[REDACTED] may be performed at interim visits for appearance of or increase/decrease in hyperemia.)

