- 2) when all patients treated with Bim SR 10 µg have completed the Month 12 visit or have exited the study prior to Month 12 (referred to as the Month 12 DBL). To provide sufficient safety follow-up data after the repeat administrations, the second database lock will occur when all patients have completed a minimum of 3 months of follow-up after the second administration or reached Month 12 without the need for the second administration; and
- 3) when all patients treated with Bim SR 10 µg have completed the Month 24 visit or have prematurely discontinued before Month 24 (referred to as the final DBL).

Analyses will be performed on unmasked data after each lock. The analysis based on the primary database lock will be considered as the primary analysis of the study. The analysis plan will support each of DBLs, but some analyses will be reduced for the final DBL (e.g, the primary efficacy analysis will not be re-produced at the final DBL).

Additional unmasked analyses based on accumulated data may be conducted after the initial Week 24 DBL (primary DBL) to support health authority submissions (e.g, 120 Day Safety Update and responses to questions). These analyses will be consisted of available data that are deemed suitable for regulatory submissions, although may not be of the quality standard used for formal, prespecified database locks.

Schedule of visits and procedures to be performed on randomized patients are presented in [Table 4-3](#) to [Table 4-7](#).

| Visit | Screening | | Baseline ^b | Day 1 (SLT Administration) | Day 2 Phone Call ^c |
|---|---------------|--|-----------------------|-------------------------------|----------------------------------|
| Visit Windows | Up to 28 days | | Up to 3 days | | |
| Pachymetry: (may be done any time after gonioscopy) | OU | | | | |
| Intraocular Pressure Hour 2 and Hour 8 (selected sites/patients^b) | | | OU | | |
| Pupil Dilation (may perform post-dilation eye exams in any order) | OU | | OU | | |
| Dilated Ophthalmoscopy | OU | | OU | | |
| Optic Disc Examination | OU | | OU | | |
| Determination of Eligibility | X | | X | X | |
| Contact Interactive Response System ^m | X | | X | X | |
| Treatment and/or Sham Administration | | | | X | |

IOP = intraocular pressure; OU = both eyes; SLT = selective laser trabeculoplasty; X = do procedure; Hour 0 = 08:00 ± 1 hour; Hour 2 = Hour 0 + 2 hours (± 30 min); Hour 8 = Hour 0 + 8 hours (± 30 min)

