11.3.5 Specular Microscopy

Endothelial cell density average (cells/mm²) will be assessed using specular microscopy performed on the central cornea of each eye at Screening, Week 4, Week 12, Week 24, Week 40, Week 52, Month 16, Month 20, and Month 24/Exit. Baseline endothelial cell density (measured at Screening), raw values, and change from baseline as well as percent changes from baseline will be summarized descriptively by visit and analysis cycle for each eye.

The number and percentage of patients will be tabulated by various thresholds (including but not limited to endothelial cell count change; e.g. $\geq 10\%$ gain, $\geq 10\%$ loss, $\geq 15\%$ loss, etc.) for the percent change from baseline at each visit and at the last visit (i.e., last visit assessment). Overall summary during the entire study and within analysis cycle will be summarized based on the greatest decrease from baseline.

Kaplan-Meier Analysis for Time to ECL Event

To further investigate the endothelial cell loss (ECL), time to event analyses will be performed on the ECL event using Kaplan-Meier (KM) method with graphical displays. The ECL event is defined as post-baseline percent loss in central corneal endothelial cell density (CECD) meeting a specified threshold. The analyses of ECL events will be performed for threshold values of $\geq 15\%$ and $\geq 20\%$. For each threshold value, *First Observed ECL* and *First Confirmed ECL* are defined as following:

1. *First Observed ECL*: The first *observed* ECL meeting the threshold is considered the initial ECL event.
2. *First Confirmed ECL*:

The first *confirmed* ECL event is defined as the first of two ECLs meeting the same threshold at two consecutive visits (scheduled or unscheduled) with CECD assessment done on different days.

- ✓ For discontinued or completed patients, if the first ECL event meeting the threshold occurs at the patient’s final CECD assessment before discontinuing/exiting the study, the loss will be counted as a confirmed loss at that date.
- ✓ For analyses performed prior to the final database lock, if a patient is continuing in the study and the first ECL meeting the threshold occurs at the

most recent CECD assessment visit before data cutoff, the loss will NOT be counted as a confirmed loss.

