The KM analyses will be performed for each of the first *confirmed* ECL and the first *observed* ECL. Compelling evidence of intra-eye variability of CECD has been observed in global, well-controlled, randomized, multicenter studies despite methodological measures in place to control for CECD variability. Therefore, the key analysis for Time to ECL Event will be based on the confirmed ECL values. For each analysis, Time (days) is calculated as follows:

- Time to the First *Confirmed* ECL event = (Date of the First *Confirmed* ECL event – Date of the First Study Treatment) + 1,
- Time to the First *Observed* ECL event = (Date of the First *Observed* ECL event – Date of the First Study Treatment) + 1,

where the Date of First Study Treatment is the first date of Bimatoprost SR 10 µg or SLT administration. For eyes that did not have any observed ECL events, time to the first ECL event will be right-censored at the last available CECD assessment date.

For each scheduled visit, the tabulation will display the number of eyes at risk, cumulative number of eyes with events, and the cumulative probability of event and the associated 95% confidence interval.

Exposure Adjusted Analysis for ECL Rate

Additionally, to take into account the differences in follow up time, an exposure-adjusted analysis for ECL rate over the entire study period will be performed by treatment for Bimatoprost SR 10 µg and SLT treated eyes. Exposure time will be calculated for each treated eye. For eyes that experienced an ECL event during the study, exposure time is the number of days from the first study treatment administration to the date when the first ECL event occurred. For eyes without an ECL event, exposure time is the number of days from the first study treatment administration to the last assessment for CECD. Exposure time in person-years is calculated as (exposure time in days)/365.25. Exposure adjusted ECL rate will be calculated per 100 person-years as:

- $100 \times (\text{number of eyes that experienced the ECL event}) / \text{total exposure time in person-years for the treatment group}$.

Listings for patients with $\geq 20\%$ CECD loss at any visit will be provided.

Coefficient of Variation Average (CV_{AVE}): Coefficient of variation average of raw data and changes from baseline will be summarized descriptively by visit and analysis cycle for each eye.

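### At the Week 24 and Month 12 locks the key confirmed endothelial cell loss curve is biased downward at its latest visits, because a continuing eye's last reading counts in the risk set but cannot carry an event

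*SAP*

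**What the plan says.** SAP 11.3.5 (Specular Microscopy) sets these rules for central corneal endothelial cell density (CECD):

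- A confirmed ECL "event is defined as the first of two ECLs meeting the same threshold at two consecutive visits (scheduled or unscheduled"; the two readings must be on different days. The event is dated at the first of the pair.
- For discontinued or completed patients, a first loss at the final assessment "before discontinuing/exiting the study, the loss will be counted as a confirmed loss at that date".
- For a continuing patient at a lock before the final one, a first loss at the "most recent CECD assessment visit before data cutoff, the loss will NOT be counted as a confirmed loss".
- Because CECD readings vary within an eye, "the key analysis for Time to ECL Event will be based on the confirmed ECL values".
- Censoring at the final CECD reading is specified for one group only: "For eyes that did not have any observed ECL events, time to the first ECL event will be right-censored at the last available". Nothing is said about an eye with an observed loss that has not been confirmed.
- In the exposure-adjusted rate, an eye without an event contributes time up to its last CECD assessment. The SAP does not say whether the event there is observed or confirmed ECL.

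Scheduled post-baseline readings are at Weeks 4, 12 and 24, and then, in Protocol 8.4.3.11, "Specular microscopy (Weeks 40 and 52 and Months 16, 20, and 24/Exit only". SAP 4.0 places the first lock when all 10 µg patients have passed Week 24 or left. It adds that "the second database lock will occur when all patients have completed a minimum of 3 months of follow-up after the second administration", or have reached Month 12 without needing one. SAP 14.0 plans a study report after each lock. SAP 12.3 repeats the ECL analyses separately for the fixed and flexible regimens.

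**The concern.** At the first two locks, the last reading of a continuing eye sits in the denominator of the confirmed curve but is barred from the numerator. An eye can lose cells, be seen to have lost them, and still add only event-free time. The effect falls on the end of the curve, which is where follow-up after a second implant lies, and the Month 12 lock was extended specifically to obtain such follow-up. It is greatest for patients who have only just reached the lock visit. Two of the three study reports would carry the biased curve, and SAP 4.0 allows further unmasked analyses after the first lock to support health authority submissions. If one regimen subgroup has fewer later readings than the other, equal risk could look unequal.

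**Working it through.** The plan states no ECL rate, ECL power or accrual period, so there is no planned figure to reproduce. From the documents come the reading schedule, the target days in SAP Tables 17-2 and 17-3, the lock definitions, 160 patients and 10% discontinuation. Everything marked as assumed is mine.

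**1. Which readings can carry a confirmed event.** This covers scheduled readings only, for a continuing patient who has just reached the cutoff.

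| Lock | Second implant | Scheduled readings after it | Able to be a confirmed event |
|---|---|---|---|
| Week 24 | Week 16 | W24 | none (0 of 1) |
| Month 12 | Weeks 16-20 | W24, W40, W52 | W24, W40 (2 of 3) |
| Month 12 | Weeks 25-32 | W40, W52 | W40 (1 of 2) |
| Month 12 | Weeks 41-51 | W52 | none (0 of 1) |

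The three-month minimum does not change the last row. Week 40 has target day 277 and Week 52 has day 361. Taking three months as 91 days, implants on days 278 to 360 reach the minimum on days 278 + 91 = 369 to 360 + 91 = 451. Month 16 has target day 477.

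**2. Bias at one visit.** Let n eyes be at risk, let L of them be continuing with their last reading there, and let a fraction h first show a persistent loss there. About hn eyes have the loss, but only h(n-L) can be confirmed, so the curve shows h(n-L)/n. With h = 3% (assumed) and n = 64:

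- L = 16: 0.03 × 48/64 = 2.25%
- L = 32: 0.03 × 32/64 = 1.5%
- L = 48: 0.03 × 16/64 = 0.75%
- L = 64: 0%, although the visit in fact provides no information on confirmed loss

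The missing censoring date does not drive this. If unconfirmed eyes were censored one reading earlier, the result would be h(n-L)/(n-hL). For L = 32 that is 0.96/(64-0.96) = 1.5%.

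**3. Cumulative illustration.** Assume persistent loss at a constant 10 per 100 eye-years.

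- Week 24, true: 1-exp(-0.1×24/52) = 4.5%. If every eye ends there, only losses seen by Week 12 count: 1-exp(-0.1×12/52) = 2.3%. If half end there, the Week 24 step of 2.28% is halved: 1-(0.9772×0.9886) = 3.4%.
- Week 52, true: 1-exp(-0.1) = 9.5%. If every eye ends there: 1-exp(-0.1×40/52) = 7.4%. If half do: 1-(0.9260×0.9886) = 8.5%.

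**4. Simulation with staggered entry.** There were 160 patients, 10% discontinuation and 150 replicates. Assumed: uniform accrual over 12, 24 or 36 months; flexible = last 40% enrolled, 60% of them re-implanted at Week 16 and the rest later; 3% persistent loss per reading after the second implant; no unscheduled readings. Flexible subgroup:

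- Week 24 lock, 24-month accrual: true 2.1%, SAP rule 1.2%, censoring at the last-but-one reading 2.0%.
- Week 24 lock, 12-month accrual: 2.0%, 0.6% and 2.6% (the last is noisy).
- Month 12 lock, to Week 52, over all accrual spans: true 7.2-7.7%, SAP rule 6.2-7.0%, re-censored 7.4-7.7%.

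The fixed subgroup showed no material difference to the same visits. With 2% false single readings and 0-20% discontinuation, the flexible subgroup at the Week 24 lock gave 1.4-1.7% under the SAP rule against 2.2-2.6% re-censored. The opposite rule for discontinued patients did not offset the bias.

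**5. Why the new cutoff must ignore unscheduled repeats.** Take h = 3%, 25% of eyes with a later scheduled reading, and half of the other losses repeated at an unscheduled visit (assumed). Events are 0.25×0.03 + 0.75×0.03×0.5 = 0.01875. If any later reading keeps an eye at risk, the risk set is 0.25 + 0.01125 = 0.26125 and the estimate is 7.2%. The SAP rule gives 1.9%. A cutoff set by scheduled readings gives 0.0075/0.25 = 3%.

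**The case against.** The confirmation rule has a stated and reasonable purpose, and most of the ECL reporting is untouched by it. At every lock the SAP also gives the first-observed ECL curve, threshold tables by visit and at the last visit, greatest-decrease summaries by cycle, and a listing of losses of 20% or more. All of these count the last reading. The final lock removes the problem. Unscheduled readings can confirm a loss, and Protocol 5.9.1.5 foresees confirmation at scheduled or unscheduled visits. All of this stands and limits the point to one display at two locks. That display is, however, the one the SAP calls key.

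Several stronger readings are tempting but not supported:

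- A reader might infer that unconfirmed eyes are followed as event-free to their last reading. The censoring sentence covers only eyes with no observed ECL; for the others the SAP is silent.
- A reader might infer that no eye re-implanted after Week 40 can be confirmed at the Month 12 lock. Three months is a minimum that every patient must meet, so patients enrolled earlier may have a Month 16 reading by cutoff.
- A reader might infer that the exposure-adjusted rate is biased. That follows only if it uses confirmed events, which the SAP does not state.
- A reader might infer that the flexible regimen will look safer. The flexible subgroup includes re-consented patients, so the enrolment order is inferred. The analyses are run separately, with no planned test. With 64 flexible eyes, a 95% interval around 7.5% is about ±6.5 points, wider than the bias at Month 12.

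The rule also applies to SLT eyes, so both treatments' rates are understated. That does not correct either one.

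**Conclusion.** The point holds for the confirmed-ECL Kaplan-Meier curve at the Week 24 and Month 12 locks, and for the exposure-adjusted rate if that uses confirmed events. The direction follows from the SAP's own wording and was the same in every scenario run. The size does not follow from the documents: it rests on assumed loss rates, persistence of loss, accrual span and frequency of unscheduled repeats. As illustrations, a visit hazard is halved when half the at-risk eyes have their last reading there. In the staggered-entry runs the flexible subgroup's cumulative figure was shown as 0.6-1.2% against about 2% at the Week 24 lock (12- and 24-month accrual), and as 6.2-7.0% against 7.2-7.7% at Week 52. A heavier effect on the flexible than the fixed subgroup is probable, not established. The documents do not support a claim that endothelial loss after the second implant is hidden from the reports as a whole. The change should be made because it is specific and cheap and concerns the analysis labelled key.

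**What to change.** In SAP 11.3.5, for locks before the final one:

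- End confirmed-ECL follow-up administratively, for every continuing patient, at the last scheduled CECD visit that is followed by another scheduled CECD reading before cutoff, whatever unscheduled repeats exist.
- Apply this to both eyes, to eyes with an observed but unconfirmed loss (which closes the censoring gap), and to the exposure-adjusted rate if it uses confirmed events. State which event that rate uses.
- Do not count confirmed events dated after that point in these analyses.

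In SAP 12.3, show the fixed and flexible confirmed curves only up to the last visit at which both have eyes at risk, and present the observed-ECL curves beside them.

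The cost is a short SAP amendment and a changed censoring date, with no new data and no delay. For patients at the lock visit, the confirmed curves end one scheduled reading earlier. A loss at that reading confirmed only by an unscheduled repeat leaves the confirmed curve at that lock, but stays in the observed curve and the tables. The lock timing does not need to change.

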11.3.6 Pachymetry

Corneal thickness using ultrasound (contact) pachymetry is performed on the central cornea for each eye at Screening, Week 4, Week 12, Week 24, Week 52, Month 16, Month 20, Month 24/Exit visits. At each examination, 3 measurements of central corneal thickness (CCT) and associated standard deviation is reported, and the average of the 3 measurements will be calculated and used for analysis. CCT raw values and their changes from baseline at each post-baseline visit will be summarized descriptively by visit and analysis cycle for each eye.

11.3.7 Biomicroscopy and Dilated Ophthalmoscopy

Biomicroscopy will be performed in each eye by slit-lamp examination at Screening, Baseline, and post-baseline visits. Dilated ophthalmoscopy examination of the vitreous, macula, and retina periphery will be performed at the Screening, Baseline, Week 12, Week 24, Week 40, Week 52, Month 16, Month 20, Month 24/Exit visits.

All findings will be coded using the MedDRA dictionary.

The Number and percentage of patient eyes with findings at least 2-grade increase in severity from baseline, or a status change from absence at baseline to presence at follow-up visit for findings which is not associated with a severity grade, at 1 or more post-baseline visits, will be summarized by preferred term in descending order of incidence rate. For findings that are associated with a severity grade, at least 2-grade increase in severity from baseline is defined as a change from no finding to 2 and above, from 0.5 to 2 and above, or from 1 to 3 and above from baseline at any of the follow-up visits.

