1.2.3 Clinical Studies with Bimatoprost SR

Study 192024-041D was a phase 1/2 paired-eye comparison study evaluating the safety and efficacy of 4 dose strengths of Bimatoprost SR (6, 10, 15, or 20 µg [2 x10 µg implants]), as single or repeat administrations in 1 eye (study eye), versus the use of topical LUMIGAN 0.03% once daily in the contralateral eye (nonstudy eye). The objective of this study was to evaluate the safety and IOP-lowering efficacy of Bimatoprost SR in patients with OAG.

A total of 109 patients received at least a single administration of Bimatoprost SR, and 24 patients received a repeat administration of Bimatoprost SR. A trend in dose response was observed across the 4 dose strengths that were tested.

Data suggest that the implant may provide topical prostaglandin analog-like efficacy up to 3 to 4 months post-implantation in the majority of patients. Data following the second administration in the retreated patients showed similar IOP lowering efficacy to that observed following the first administration of Bimatoprost SR. In addition, efficacy was maintained longer than the expected 3- to 4-month duration in many patients in this completed study. By Month 6, most patients (> 66%) were still maintained on monotherapy with the initial Bimatoprost SR implant administered. Among all Generation 2 dose strengths, at least 33% of patients had not received rescue or a second Bimatoprost SR treatment by Month 12. At Month 24, at least 23% of patients had not received rescue or a second treatment.

Bimatoprost SR showed an acceptable safety profile with single and repeat administrations in study 192024-041D. Most adverse events were ocular, mild or moderate in severity, occurred within the first 2 days after Bimatoprost SR administration, and were considered related to the study drug administration procedure. There were no reports of serious study drug-related adverse events, and no new safety concerns were observed after the second treatment. Please refer to the Investigator's Brochure for details on reported safety findings.

Two identical global phase 3 studies (Studies 192024-091 and 192024-092) were initiated in late 2014. These studies are assessing the safety and efficacy of Bimatoprost SR in multicenter, randomized, masked, parallel-group comparison studies of 2 dose strengths of Bimatoprost SR (10 and 15 µg) to an active control (timolol maleate 0.5%).

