 - i.e, Ocular TEAEs that occur within two days from the Bim SR treatment for the Bim SR eye and/or (Bim SR sham for the SLT eye)
- Any ocular TEAEs after two days of study treatment by SOC and PT
 - i.e, Ocular TEAEs that occur after two days from the Bim SR treatment for the Bim SR eye and/or (Bim SR sham for the SLT eye) to next Bim SR/ Sham Bim SR treatment (Bim SR sham for SLT eye)
- SLT procedure related ocular TEAEs by SOC and PT
 - i.e, Ocular TEAEs that occur starting from Day 1, but before the first Bim SR treatment will be summarized.

- Any corneal TEAEs of interest by SOC and PT (Corneal AEs of interest will be identified separately prior to database lock.)
- Any anterior segment inflammation TEAEs of interest by SOC and PT (Anterior segment inflammation AEs will be identified separately prior to database lock.)

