17.3 ANALYSIS WINDOWS

[Table 17-1](#) provides an overview of efficacy and safety assessments with visit schedule and analysis window table for by-visit and by-cycle analysis.

Table 17-1 Visit Schedule, Visit Windows and By-Cycle Analysis for Efficacy and Safety Assessments

| Efficacy/Safety Assessments | Visit Schedule | Visit Window for by-visit and Analysis Cycle Analysis |
|---|--|--|
| Hour 0 IOP | Baseline, Day 2, W4, W8, W12,W15, W20,W24,W28,W31,W36,W40,W44, W47,W52, M13, M14,M15,M16,M18, M20,M22, M24/EXIT | Table 17-2 |
| Macroscopic conjunctival hyperemia | Baseline, Day2, W4,W8,W12,W15, W20,W24,W28,W31,W36,W40,W44,W47 ,W52,M13,M14,M15,M16,M18,M20,M22 , M24/EXIT | Table 17-2 |
| BCVA | Baseline, Day 2, W4, W8, W12, W15, w20,W24,W28,W31,W36,W40,W44, W47,W52,M13,M14,M15,M16,M18,M20, M22,M24/EXIT | Table 17-2 |
| Visual field | Baseline, W24,W52,M18,M24/exit | Table 17-4 |
| Specular microscopy | Baseline, W4, W12, W24, W40, W52,M16,M20, M24/Exit | Table 17-3 |
| Biomicroscopy | Baseline, Day2, W4, W8,W12,W15, W20,W24,W28,W31,W36,W40,W44, W47,W52, M13,M14,M15,M16,M18, M20,M22, M24/EXIT | Overall by-cycle summary |
| Gonioscopy/ Angle assessment | Baseline,W4(optional),W8,W12(optional), W15,W20,W24(optional),W28,W31,W36, W40,W44,W47,W52,M13,M14,M15,M16, M18,M20,M22,M24/EXIT | Table 17-2 |
| Pachymetry | Baseline, W4, W12, W24, W40, W52, M16, M20, M24/EXIT | Table 17-3 |
| Optic disc/ Ophthalmoscopy/ Lens assessment | Baseline, W12, W24, W40, W52, M16, M20, M24/EXIT | Table 17-3 |

[Table 17-2](#) presents the visits assigned for by- visit and analysis cycle analyses of the efficacy (Hour 0 IOP), and safety assessments that occur every month (or 2 months after 1-year of follow-up after the first Bim SR administration), including of macroscopic conjunctival hyperemia, best-corrected visual acuity, biomicroscopy, and gonioscopy/angle assessment. [Table 17-3](#) presents the visit assigned for by-visit and analysis cycle that occur every 3 or 4 months, including of specular microscopy, pachymetry and optic disc assessments which occur every 3 or 4 months. [Table 17-4](#) presents the visits assigned for by-visit and analysis cycle analyses of visual filed, ophthalmoscopy, optic disc, and lens assessments which occur every 6 months.

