If both scheduled and unscheduled visit occur within a single window, the scheduled visit will be used; and unscheduled visits will be used only if there are no scheduled values available in that window. If multiple visits are eligible for windowing within a single visit window, the scheduled visit closest to target day will be used in the analysis.

If 2 visits are equidistant to the target day, the later visit will be used.

Table 17-2 Visit Windows for By Visit Analysis for Assessments Occurring Every 4 weeks

| Derived Visit | Target Visit Day* | Visit Window* |
|-----------------------------------|---|---|
| Baseline ^a | -1 | ≤ (SLT Date -1) |
| Analysis Cycle 1 | | |
| Cycle 1 SLT Day 1 | 1 | SLT Date |
| Cycle 1 Bim SR Day 1 ^b | Bim SR 1st administration, Day 1 | Bim SR 1st administration, Day 1 |
| Cycle 1 Bim SR Day 2 ^b | Bim SR 1st administration, Day 1 + 1 | Bim SR 1st administration Day 1 + 1 |
| Cycle 1 Week 4 | 25 | [Bim SR 1st administration, Day 1+2, 38] |
| Cycle 1 Week 8 | 53 | [39, 66] |
| Cycle 1 Week 12 | 81 | [67, 91] |
| Cycle 1 Week 15 | 102 | [92,119] |
| Cycle 1 Week 20 | 137 | [120, 150] |
| Cycle 1 Week 24 | 165 | [151, 178] |
| Cycle 1 Week 28 | 193 | [179, 203] |
| Cycle 1 Week 31 | 214 | [204, 231] |
| Cycle 1 Week 36 | 249 | [232, 262] |
| Cycle 1 Week 40 | 277 | [263, 290] |
| Cycle 1 Week 44 | 305 | [291, 315] |
| Cycle 1 Week 47 | 326 | [316, 343] |
| Cycle 1 Week 52 | 361 | [344,373] |
| Cycle 1 Month 13 ^c | 387 | [374,401] |
| Cycle 1 Month 14 | 417 | [402,431] |
| Cycle 1 Month 15 ^c | 447 | [432,461] |
| Cycle 1 Month 16 | 477 | [462,506] |
| Cycle 1 Month 18 | 537 | [507,566] |
| Cycle 1 Month 20 | 597 | [567,626] |
| Cycle 1 Month 22 ^c | 657 | [627,686] |
| Cycle 1 Month 24 | 717 | >686 |
| Analysis Cycle 2 ^d | | |
| Cycle 2 Bim SR Day 1 | 1 | Bim SR 2nd administration, Day 1 |
| Cycle 2 Bim SR Day 2 | 2 | Bim SR 2nd Administration Day 1 + 1 |
| Cycle 2 Week 4 | 29 | [Bim SR 2nd administration, Day 1+2, 42] |
| Cycle 2 Week 8 | 57 | [43, 70] |
| Cycle 2 Week 12 | 85 | [71, 98] |
| Cycle 2 Week 16 | 113 | [99,126] |
| Cycle 2 Week 20 | 141 | [127,154] |
| Cycle 2 Week 24 | 169 | [155, 182] |
| Cycle 2 Week 28 | 197 | [183,210] |
| Cycle 2 Week 32 | 225 | [211, 238] |
| Cycle 2 Week 36 | 253 | [239, 266] |

| | | |
|-------------------------------|--|---|
| Cycle 2 Week 40 | 281 | [267, 294] |
| Cycle 2 Week 44 | 309 | [295, 322] |
| Cycle 2 Week 48 | 337 | [323,350] |
| Cycle 2 Week 52 | 365 | [351, 377] |

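### The SAP's biomicroscopy summary merges findings from the day after administration with later ones, and the SAP contradicts itself on by-visit output

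*SAP*

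**What the plan says.** SAP 11.3.7 summarizes biomicroscopy by preferred term. An eye counts if it has a qualifying finding "at 1 or more post-baseline visits, will be summarized by preferred term in descending order of incidence rate". For graded findings the threshold is "a change from no finding to 2 and above, from 0.5 to 2 and above, or from 1 to 3 and above"; an ungraded finding qualifies when it is absent at baseline and present later.

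The biomicroscopy row of SAP Table 17-1 includes Day 2 among the visits. Table 17-2 sets the target for that visit in Cycle 1 at "Bim SR 1st administration, Day 1 + 1", the day after the implant is given (not the telephone call on the day after laser). SAP 11.0 presents ocular safety for the whole study, Analysis Cycle 1 and Analysis Cycle 2. Each cycle contains an administration and its next-day examination.

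On presentation, the biomicroscopy row of Table 17-1 reads "Overall by-cycle summary". The text below that table says Table 17-2 serves the by-visit and cycle analyses of monthly assessments, "including of macroscopic conjunctival hyperemia, best-corrected visual acuity, biomicroscopy, and gonioscopy/angle assessment".

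For adverse events, SAP 11.1 has separate tables within and after two days of treatment. The later one covers "Ocular TEAEs that occur after two days from the Bim SR treatment for the Bim SR eye" and the matching period after sham in the SLT eye.

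**The concern.** Slit-lamp examination is the scheduled assessment that looks at both the cornea and the anterior chamber at every follow-up visit. For an implant that stays in the anterior chamber for months, the useful question is whether findings after the procedural period are more frequent in Bim SR eyes than in SLT eyes. An any-visit count that includes the day after needle entry does not answer it. A moderate finding gone by Week 4 and one that persists for months are the same entry.

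The by-cycle split does not help, because every cycle starts with its own procedure. The SAP treats the first two days as special elsewhere: SAP 11.1 splits ocular adverse events there, and SAP 10.3.2 leaves early IOP readings out of the onset analysis. In the completed phase 1/2 study described in Protocol 1.2.3, most adverse events "occurred within the first 2 days after Bimatoprost SR administration, and were considered related to the study drug administration procedure".

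**Working it through.** The plan states no figure for biomicroscopy, so there is nothing to reproduce. The check has two parts.

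**Comparing the texts**

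- *Is the next-day examination counted?* Yes. It is a post-baseline visit under 11.3.7, is listed in the Table 17-1 row, and falls inside the cycle under 11.0.
- *Are the two eyes alike on that day?* No. Under Protocol 5.9.1.3 the sham applicator has no needle and does not enter the anterior chamber. In Cycle 1 the SLT eye had laser on Day 1, about four days before this examination, so it may carry procedural findings of its own.
- *Is by-visit output planned?* The documents conflict. The Table 17-1 row gives no window table, 11.3.7 specifies no by-visit table, and the text below Table 17-1 assigns biomicroscopy to Table 17-2. In Table 17-2, Day 2 is its own visit and the Week 4 window opens on the following day. If that text governs, by-visit output would separate the procedural examination.
- *Is dilated ophthalmoscopy affected?* Not by this mechanism. Its first scheduled examination after treatment is at Week 12.

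**Illustration for one preferred term (all rates assumed)**

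Let p be the probability of a qualifying finding at the next-day examination in a Bim SR eye. Let qB and qS be the probabilities of a late finding in the Bim SR and SLT eye. Early and late findings are taken as independent within an eye, and the SLT eye is given no procedural findings.

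- Any-visit rate, Bim SR: 1 − (1 − p)(1 − qB)
- The same with no late excess: 1 − (1 − p)(1 − qS)
- Contribution of the late excess: (1 − p)(qB − qS)
- Share of counted Bim SR eyes with a next-day finding only: p(1 − qB) / [1 − (1 − p)(1 − qB)]

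For p = 30%, qB = 10%, qS = 3%: 1 − 0.70 × 0.90 = 37.0%; 1 − 0.70 × 0.97 = 32.1%; contribution 0.70 × 7 = 4.9 points; share 0.27 / 0.37 = 73%. On 160 eyes that is about 59 against 51.

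| p | Any-visit rate, late 10% | Any-visit rate, late 3% | Contribution of late excess (points) | Next-day only |
|---|---|---|---|---|
| 5% | 14.5% | 7.85% | 6.65 | 31% |
| 10% | 19.0% | 12.7% | 6.3 | 47% |
| 20% | 28.0% | 22.4% | 5.6 | 64% |
| 30% | 37.0% | 32.1% | 4.9 | 73% |
| 50% | 55.0% | 51.5% | 3.5 | 82% |

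A table restricted to later examinations would show 7 points in every row. With late rates of 5% and 2%, the 3-point excess contributes 0.95 × 3 = 2.85 down to 0.50 × 3 = 1.5 points, and 49% to 90% of counted eyes have a next-day finding only.

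If the SLT eye has procedural probability r and both eyes share a late rate q, the any-visit difference is (p − r)(1 − q). The table can thus show a difference with no late difference at all. Setting r = 0, as above, favours the concern.

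**The case against.** The strongest reply is that an any-visit count is a legitimate worst-case summary, that no hypothesis or decision rule depends on it, and that the plan looks for late harm elsewhere. All of that stands. SAP 11.1 tabulates ocular adverse events after two days by eye and cycle, plus corneal and anterior segment inflammation events of interest. SAP 11.3.5 gives cell density by visit and time to confirmed loss, 11.3.6 gives corneal thickness by visit, and 11.3.10 gives implant contact with the endothelium by cycle. SAP 17.5 lists every assessment.

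Two features of 11.3.7 also narrow the effect. The 2-grade rule already removes new trace and mild graded findings. Tabulation by preferred term means that a late finding under a different term is still counted.

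The cover is partial. The adverse event tables depend on a finding being recorded as an event, and the primary investigator is unmasked (Protocol 9.4). Cell density and pachymetry concern the central cornea and do not register anterior chamber inflammation. Listings do not compare eyes. In fairness, the specific masked-examiner rules in Protocol 6.1.1 and 8.4 concern IOP, so a revised slit-lamp table may share the limitation of unmasked assessment.

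A reader might infer that the plan reports biomicroscopy only as ever present and so hides late corneal or inflammatory harm. The documents do not support that. The text under Table 17-1 points to by-visit analysis, the late excess is diluted rather than removed, and the other outputs remain. Nor does Protocol 1.2.3 state what is expected in this trial: it reports adverse events from an earlier study, not slit-lamp grades.

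**Conclusion.** The point holds as a modest weakness in a descriptive safety table. Within a preferred term, 11.3.7 merges procedural and late biomicroscopy findings, and needle entry makes the merging uneven between the eyes. A late excess in Bim SR eyes would be diluted by the factor (1 − p) and could not be told apart from procedural findings. Because p and the late rates are assumptions, the table under working shows how the summary behaves and predicts nothing for this trial. A pooled figure across all findings would not describe the planned table either, since 11.3.7 reports by preferred term.

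The conflict between the Table 17-1 row and the text below it rests on no assumption and needs correcting in any case. The primary efficacy conclusion is unaffected.

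**What to change.** 1. Reconcile the biomicroscopy row of Table 17-1, the text below that table, and 11.3.7, so that all three state the same output.
2. In 11.3.7, report biomicroscopy findings by preferred term, eye and analysis cycle, separately for (a) examinations within two days of an administration and (b) any later examination. This follows the two-day split of SAP 11.1. Keep the post-laser Day 1 examination in the procedural period as well. State how the two days are counted, because the Table 17-2 Week 4 window opens two days after the administration date.
3. For corneal and anterior chamber findings, add the percentage of eyes affected at each visit, using the Table 17-2 windows. The split alone would not show persistence, since a single Week 4 finding and one lasting months would both fall under (b).

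The data are already collected and the windows exist. The cost is SAP wording and one or two more descriptive tables.
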